Title: Threat Interpretation Bias as Cognitive Marker and Treatment Target in Pediatric Anxiety: R61 Phase

NCT NUMBER: NCT04245501

Revised document date: 02/20/2020

PROJECT SUMMARY AND SPECIFIC AIMS:

Anxiety is the most common mental health problem in youth, affecting one in four children and adolescents. Unfortunately, evidence-based interventions (pharmacotherapy, cognitive-behavioral therapy) are costly, not widely available, and ineffective for a substantial proportion (~50%) of youth. In response, experts have called for novel *treatments that directly target mechanisms underlying youth anxiety* while simultaneously addressing barriers to care (i.e., cost, accessibility). One such promising mechanism is interpretation bias - the inaccurate interpretation of threat from ambiguity. We have previously demonstrated that interpretation bias occurs in over 90% of anxious youth, accounts for 46% of variance in anxiety severity above and beyond demographic and clinical characteristics, and differentiates between anxious and non-anxious youth. These data indicate that *interpretation bias is a ubiquitous phenomenon underlying anxiety expression in children and adolescents* and therefore may be an *ideal intervention target*. Cognitive bias modification for *interpretation bias* (CBM-I) is a computerized intervention that attempts to reduce anxiety symptoms by directly modifying interpretation bias; participants are provided with real-time corrective feedback when they select threat-relevant interpretations of ambiguity. CBM-I has demonstrated preliminary efficacy for reducing anxiety symptoms in adults. Yet extant CBM-I data in youth are sparse, and several critical questions have not been answered: 1) is the targeted mechanism (interpretation bias) modified by CBM-I in youth?; 2) what dose reflects meaningful interpretation bias change?; and 3) is interpretation bias reduction the mechanism underlying anxiety symptom reduction? Consistent with NIMH strategies to “define mechanisms” and “accelerate therapeutics”, we propose to test interpretation bias as a putative intervention target. This proposal includes a two-phased study of *personalized* CBM-I in youth ages 10 to 17 who meet diagnostic criteria for anxiety disorder (generalized, social, separation). In the R61 Phase (N=46), an RCT examines whether CBM-I personalized to youth anxiety symptoms engages the interpretation bias target, compared to a computerized interpretation control condition (ICC). Our Go/No-Go Milestones reflects a significant difference in interpretation bias reduction between groups (CBM-I outperforms ICC). The interpretation target will be measured at multiple time points (4, 8, 12, 16 sessions) to identify the optimal dose for target engagement.

Aim 1: Directly engage and modify interpretation bias. *We predict that, compared to ICC, personalized CBM-I will result in significantly greater reduction of interpretation bias on at least two of three measures: objective linguistic interpretation bias via a word-sentence association paradigm^{6,7}, objective visual interpretation bias via an ambiguous faces task¹², subjective questionnaire of threat attributions.¹³*

Aim 2: Determine CBM-I dose for R33 Phase and subsequent trials. *Dosing is a critical issue relevant to target validation. Interpretation bias will be assessed at four CBM-I doses (4, 8, 12, 16 sessions) in order to identify the optimal dose at which bias reduction occurs.*

Aim 3: Ascertain feasibility and acceptability of approach. *We predict that CBM-I will be feasible with youth, and acceptable to youth and parents.*

R61 GO/NO-GO MILESTONES FOR R33 PHASE:

To proceed to the R33 Phase, CBM-I in the R61 Phase must meet the following criteria:

- 1) **target engagement** on at least two of three interpretation bias outcomes (described above) as reflected by a significant medium effect ($d=0.50$) between groups from pre-to-post-intervention.
- 2) be **feasible** in regards to administration (average of 90% training sessions completed) and rated as **acceptable** (average score of 30 out of 50 on self-reported exit interview¹⁴) to youth and parents.

STATISTICAL ANALYSIS PLAN:

Aims 1 and 2. Multilevel modeling (using Mplus 8.4 [Muthén & Muthén, 2022] software) will examine changes in interpretation bias assessed via both objective (word-sentence association paradigm [WSAP], ambiguous face task [FACES]) and subjective (CATS) measures. Given that some enrolled participants may be siblings, we will adjust all analyses for within-family correlations. In order to estimate the importance of modeling the family-level variance separately from the person-level variance, we will first estimate the Intraclass Correlation Coefficient (ICC) for the three-level model of each target outcome as the proportion of the between-person variability that is between families = (Level 3 variance)/(Level 3 + Level 2 variance). Three-level models will be utilized for outcomes where ICC is high, and two-level model (i.e., observations at level 1 clustered within individuals at level 2) for low ICC that adjust standard errors chi-square statistics for the family-level clustering, using TYPE=TWOLEVEL COMPLEX analysis in Mplus (Muthén & Satorra, 1995).

For each target outcome, multilevel models will test the effects of CBM-I vs ICC group on changes in the outcome. Given that bias change over time may not occur in a linear fashion, we will compare several alternative models for change over time. For the interpretation bias outcomes (assessed at training sessions 1, 5, 9, 13, and one-week post session 16), we will test a *linear model* of change, a *quadratic model*, a *piecewise model that estimates change with two slopes* – one specifying the early rate of changes in the outcome (between training sessions 1 and 9) and the second specifying the rate of change that occurs during later sessions (starting from session 9 to one-week post session 16), and a *piecewise model that estimates changes with three slopes* – one specifying early rate of changes in outcome (between training sessions 1 and 5), the second specifying rate of change that occurs during middle sessions (between sessions 5 and 13, and the third specifying rate of change that occurs during later sessions (starting from session 13 to one-week post session 16). Once the best-fitting model is identified for each outcome, the treatment group will be used to predict between-individual differences in slopes.

Aim 3. In regards to treatment completion and feasibility, we will examine the percentage of youth who completed all 16 trainings, and the proportion of trainings completed by youth who did not complete all 16 trainings. In regard to acceptability, youth and caregivers will complete the Participant/Parent Acceptability Questionnaire and Exit Interview (PAQ). The PAQ assesses how much computer tasks (i.e., bias assessments and trainings) made participants feel tired or bored, whether the computer trainings helped the youth feel less worried, nervous, scared or stressed, whether it was difficult to remember to complete at-home trainings, barriers to participation (i.e., travel, time off work/school, etc.), an overall/global rating for their experience with the study, and whether they would recommend the study to a friend. PAQ total scores range from 0 to 50, with higher scores indicating higher acceptability of the computerized intervention and related training session procedures. Scores of 30-39 indicate at least moderate acceptability, with scores of 40-50 indicating high acceptability. Given that CBM-I and ICC may be associated with differential acceptability, we will also compare acceptability ratings for youth and caregivers between randomized groups with t-tests.

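### Milestone 1 needs a significant pre-to-post d of 0.50, but the planned slope models never form that contrast and no SD is named for d

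*Combined protocol and SAP*

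**What the plan says.** Three places describe target engagement, and a fourth describes the analysis that would establish it.

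- **R61 Go/No-Go Milestones for R33 Phase, criterion 1**, the list that must be met to proceed: engagement on two of three bias outcomes, "as reflected by a significant medium effect ($d=0.50$) between groups from pre-to-post-intervention".
- **Project Summary and Specific Aims**: "Our Go/No-Go Milestones reflects a significant difference in interpretation bias reduction between groups". No d is given.
- **Aim 1**, worded as a prediction: CBM-I "will result in significantly greater reduction of interpretation bias on at least two of three measures". No d is given.
- **Statistical Analysis Plan, Aims 1 and 2**: linear, quadratic, two-slope and three-slope models are compared for each outcome over five assessments (sessions 1, 5, 9, 13 and one week after session 16). Once the best-fitting one is found, "the treatment group will be used to predict between-individual differences in slopes".

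The documents do not state which SD divides the difference to give d, whether 0.50 is a minimum for the estimate, the alpha level or sidedness, how slopes become a pre-to-post effect, or which slope decides when there are two or three.

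**The concern.** The milestone and the analysis concern different quantities. The milestone is about one standardised difference between two time points. The analysis yields between one and three slope differences, on the scale of the measure, from a model selected on the data. Moving from one to the other takes at least two decisions that the plan leaves open: which combination of slopes counts, and which SD goes in the denominator.

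This criterion helps decide whether the R33 phase proceeds. If those decisions are made once the estimates are known, the same data could be reported as meeting or missing the threshold. A significant early slope could also be counted as engagement although the gain had gone by the post-intervention assessment.

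**Working it through.** **1. No plan figure to reproduce.** The documents give N=46 and d=0.50 but no power, alpha, SD or sample-size calculation.

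**2. The missing contrast.** Code time as sessions completed: 0, 4, 8, 12, 16. Let b be the group difference in each time coefficient. The pre-to-post group difference is then:

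- linear: 16b
- quadratic: 16b1 + 256b2
- two slopes: 8b1 + 8b2
- three slopes: 4b1 + 8b2 + 4b3

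Only in the linear model is the test of the slope also the test of the pre-to-post difference. As an illustration, take a two-slope model with b1 = 0.0625 and b2 = -0.0625 session-1 SDs per session. CBM-I leads by 8 × 0.0625 = 0.50 at session 9, yet the pre-to-post difference is 0.50 - 0.50 = 0. A significant b1 would satisfy the planned test but not the milestone.

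**3. The missing SD.** Assumptions, none of them in the documents: 23 per arm, two-sided 5%, no dropout, no sibling clustering, linear random-slope model, intercept and slope uncorrelated, session-1 SD 1. Let e be the residual share of the session-1 variance (0.2, 0.3, 0.4, 0.5) and s the SD of individual slopes over the whole course (0.3, 0.5, 0.7, 0.9), giving 16 settings. With time scaled 0 to 1 over five equally spaced points:

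- group on slope only: SE² = (2/23)[s² + 1.6e - (0.8e)²/(1 - 0.4e)]
- group intercept added: SE² = (2/23)[s² + 1.6e]
- smallest significant difference m = 2.015 × SE (t, 44 df)
- SD of the pre-to-post change = √(s² + 2e)

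Example, s=0.3 and e=0.2, group on slope only: SE² = (2/23)(0.09 + 0.32 - 0.0256/0.92) = 0.0332, SE = 0.182, m = 0.367. The change SD is √0.49 = 0.70.

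Smallest significant difference in session-1 SDs, group on slope only:

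| s | e=0.2 | e=0.3 | e=0.4 | e=0.5 |
|---|---|---|---|---|
| 0.3 | 0.367 | 0.422 | 0.463 | 0.494 |
| 0.5 | 0.438 | 0.484 | 0.521 | 0.548 |
| 0.7 | 0.526 | 0.565 | 0.597 | 0.620 |
| 0.9 | 0.624 | 0.658 | 0.685 | 0.706 |

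- **Session-1 SD:** 0.37-0.71; below 0.50 in 6 of 16 settings, or 3 of 16 with a group intercept.
- **Change SD:** m/√(s² + 2e) is 0.47-0.57; below 0.50 in 3 of 16, and in none with a group intercept (0.54-0.57).
- **Random-slope SD:** m/s is 0.69-1.65; never below 0.50.

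One estimate on three scales, at s=0.3 and e=0.2: a difference of 0.45 session-1 SDs is significant (0.45/0.182 = 2.47). It is d = 0.45 on the session-1 SD, 0.45/0.70 = 0.64 on the change SD and 0.45/0.3 = 1.5 on the random-slope SD. It fails the threshold on the first scale and passes on the other two.

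**4. Effect on one measure, true d = 0.50 on the session-1 SD.** P(significant) = Φ(0.50/SE - 2.015). P(significant and d at least 0.50) = Φ((0.50 - max(m, 0.50))/SE).

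- s=0.3, e=0.2: Φ(2.743 - 2.015) = 77% versus 50%
- s=0.3, e=0.3: 64% versus 50%
- s=0.3, e=0.5: 51% versus 50%
- s=0.7 or 0.9: no difference, because m already exceeds 0.50

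**5. Cross-check with two time points.** A change-score t-test with 23 per arm has smallest significant d = 2.015 × √(2/23) = 0.594 in change SDs. In session-1 SDs, with equal SDs at both times, this is 0.594 × √(2(1 - r)), where r is the pre-post correlation: 0.532 at r=0.6, 0.460 at 0.7, 0.376 at 0.8. It falls below 0.50 once r exceeds about 0.65, or about 0.54 with baseline adjustment, where the factor is √(1 - r²). In simulation of the change-score test (40,000 trials per setting, true d 0.50 in session-1 SDs), significance alone and significance with d at least 0.50 gave different answers in about 9% of trials at r=0.7 and 24% at r=0.8.

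**The case against.** **The milestone list governs.** A reader might infer that the documents hold competing Go rules, so that a significant d of 0.45 is Go by the summary or Aim 1 and No-Go by the milestone. The documents do not support that. The milestone list is the only operative rule. The summary sentence abbreviates it, also leaving out the two-of-three count, feasibility and acceptability. Aim 1 is a hypothesis. This objection stands, and the missing d in those two places is a matter of aligning the wording. It does not repair the milestone, which still cannot be computed from the planned models as written.

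**Significance already implies 0.50.** With d in change-SD units and a simple change-score test, the smallest significant d is 0.594, so the threshold adds nothing. The same holds across the grid for the change SD when a group intercept is fitted, and the plan does not exclude one. On the session-1 SD the threshold adds nothing in 10 of 16 settings. This also stands: any divergence is conditional, and the 77% versus 50% comparison is the extreme of the grid. But whether the threshold matters turns on a denominator that the plan does not name.

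**The inputs are assumed.** They are. Dropout, for instance, would raise the smallest significant d (0.640 with 20 per arm in the two-time-point test). No figure is claimed here for the two-of-three rule, which would need the correlation among the measures.

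**Conclusion.** The concern holds as a gap between the milestone and its analysis. The missing contrast needs no variance assumption: under the quadratic and piecewise models the planned slope tests do not test the pre-to-post difference, and in a piecewise model a significant slope can coexist with no such difference. Under the linear model the contrast is implied and only the SD is missing.

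The size of the SD problem is conditional on the assumptions in the working. For one measure, adding the 0.50 condition on the session-1 SD lowers the chance of passing by anything from nothing to 27 percentage points (77% to 50%). On the change SD the threshold scarcely binds, and on the random-slope SD it never does. It would go too far to say that conflicting decisions are likely. What the documents support is that the decision rests on choices not fixed in advance, which is worth correcting because it bears directly on whether the R33 phase proceeds.

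**What to change.** In milestone 1 and the Statistical Analysis Plan, define target engagement for each measure as follows:

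- The estimate is the model-implied CBM-I minus ICC difference in change from session 1 to one week after session 16, whichever time model is selected.
- It favours CBM-I and is significant at a stated two-sided alpha.
- Divided by the pooled session-1 SD, it is at least 0.50 in size.

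Report d with its 95% confidence interval. Keep the two-of-three count. Use the individual slope tests for the Aim 2 dose question only. Align the summary and Aim 1 with this wording.

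The cost is text only: no further participants or assessments, and the contrast is a linear combination of coefficients already estimated. The downside is that Go becomes somewhat harder to reach than under significance alone when the pre-post correlation is high.

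### None of the four planned time curves leaves the CBM-I minus control difference free at all four session doses; for Aim 2, report the four categorical-time contrasts beside the selected curve

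*Combined protocol and SAP*

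**What the plan says.** The Project Summary gives the purpose of the repeated assessments: "The interpretation target will be measured at multiple time points (4, 8, 12, 16 sessions) to identify the optimal dose for target engagement". Aim 2 says that bias will be "assessed at four CBM-I doses (4, 8, 12, 16 sessions) in order to identify the optimal dose at which bias reduction occurs". The Go/No-Go Milestones define target engagement as an effect "between groups from pre-to-post-intervention".

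Under Aims 1 and 2 of the Statistical Analysis Plan, the outcomes are "assessed at training sessions 1, 5, 9, 13, and one-week post session 16", that is, a baseline and four later occasions. The plan then states that "we will compare several alternative models for change over time" and lists four: linear, quadratic, two slopes joined at session 9, and three slopes joined at sessions 5 and 13. In the last of these the middle segment is described as "the second specifying rate of change that occurs during middle sessions (between sessions 5 and 13". Group comes in afterwards: "Once the best-fitting model is identified for each outcome, the treatment group will be used to predict between-individual differences in slopes".

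The plan does not name the fit criterion, list which growth terms are random, or give the time code for the final visit. It writes no between-group contrast at each dose and no rule for turning slopes into a dose.

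**The concern.** Comparing four doses on a between-group effect requires four differences that the data can move independently. A growth curve with fewer group-by-time parameters ties some of those differences together by assumption. Part of the answer at a given dose then comes from the shape of the curve and not from the children assessed at that dose. The curve is also picked before group is in the model, so a shape that suits overall change need not suit the difference between arms.

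The result of Aim 2 is meant to set the dose for the R33 phase and later trials. If the selected curve has the wrong shape for the group difference, the interval at an early dose can be both misplaced and too tight. Nothing else in the planned output would show it.

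**Working it through.** The plan states no figure for this point, so there is nothing to reproduce. The check has four steps.

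**Inputs from the documents.** Assessments at sessions 1, 5, 9, 13 and one week after session 16; doses 4, 8, 12, 16; the four curves; group on slopes only; N=46.

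**Assumptions not in the documents.** 23 per arm; SD 1; correlation 0.6 between any two assessments; no siblings or missing data; assessments at sessions 5, 9 and 13 reflect 4, 8 and 12 completed sessions. Time is session number minus 1, with the final visit coded 17 (equal spacing) unless stated.

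**Step 1: count free differences.** With x = time since baseline, D(x) is the sum of the group coefficients times the curve's time terms. The number of free differences over the four doses is the rank of those terms.

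| Curve | Time terms | Rank (4 needed) |
|---|---|---|
| Linear | x | 1 |
| Quadratic | x, x² | 2 |
| Two-slope | min(x,8), max(x−8,0) | 2 |
| Three-slope | min(x,4), x−4 limited to 0–8, max(x−12,0) | 3 |
| Categorical | four indicators | 4 |

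The ranks are the same with the final visit coded 16, 17, 18 or 20. If group is also put on the intercept, the ranks for change from baseline remain 1, 2, 2 and 3.

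**Step 2: the ties.** In the three-slope curve, D(8) = w·D(4) + (1−w)·D(12), where w = (t13 − t9)/(t13 − t5) and t is the time code of that session. With session numbers w = (13−9)/(13−5) = 0.5, a plain average; under calendar time it is a weighted average. In the two-slope curve with session-number time, D(4) = (4/8)·D(8), half of dose 8. Dose 12 falls midway between 8 and 16 only if the final visit is coded as equally spaced.

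**Step 3: what each curve returns.** The generalised least squares fit is b = (X′R⁻¹X)⁻¹X′R⁻¹D, where X holds the curve's time terms, R is the assumed correlation matrix and D the true differences. Fitted differences at doses 4, 8, 12, 16:

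| Curve | Truth 0, 0.6, 0.6, 0.6 | Truth 0.6 throughout | Truth 0.3, 0.6, 0.6, 0.6 |
|---|---|---|---|
| Linear | 0.18, 0.36, 0.54, 0.72 | 0.14, 0.29, 0.43, 0.57 | 0.16, 0.32, 0.48, 0.65 |
| Quadratic | 0.29, 0.50, 0.63, 0.69 | 0.40, 0.61, 0.65, 0.50 | 0.34, 0.55, 0.64, 0.60 |
| Two-slope | 0.29, 0.57, 0.63, 0.68 | 0.31, 0.63, 0.57, 0.52 | exact |
| Three-slope | 0.10, 0.40, 0.70, 0.60 | exact | 0.35, 0.50, 0.65, 0.60 |
| Categorical | exact | exact | exact |

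Two mechanisms appear. The first shape lies outside all four curves. The second and third lie inside one curve each, so error there arises only if selection before group is added picks another curve.

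**Step 4: interval width.** The dose-4 standard error is 0.053 for the linear curve and √[(2/23)(1 − 0.6²)] = 0.236 for the categorical model. Under the first shape the linear interval is centred on 0.18 ± 1.96 × 0.053, or 0.08 to 0.28, where the truth is 0. The three-slope interval is wider (standard error 0.223 at dose 4), but its estimates peak at dose 12 when the true difference is level from dose 8.

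**Simulation of the whole sequence** (curve chosen on pooled arms by AIC or BIC, then group added; random intercept; 1,500 trials per case). Under the first shape, the nominal 95% CI covered the truth in 11–55% of trials at dose 4 and 45–89% at dose 8, against 94–95% for the categorical model. With a plateau from dose 4, dose-4 coverage was 18–53% if the control arm does not change and 85–91% if it improves by 0.5 SD. With a steady rise to dose 8, dose-8 coverage was 39–62% and 87–93% respectively. If change is truly linear, there was no bias and coverage was 93–95%.

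**The case against.** Segmented growth curves are a legitimate way to describe when change happens. Aim 2's wording can be read as asking just that, and early, middle and late slopes speak to it directly. That stands, and is why the curves should be kept. But one slope spans doses 4 to 12 in the three-slope curve, and another spans baseline to dose 8 in the two-slope curve. A choice between adjacent doses within a segment still rests on an assumed straight line. The Project Summary also ties the optimal dose to target engagement, which the milestones define between groups.

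The size is open to challenge. The plan implies slopes that vary between children. With true slope variation (SD 0.6–0.8 over the trial, assumed), a linear random-slope fit covers dose 4 in about 26–38% of trials under the first shape, against 8% without it. That is better but still poor.

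The categorical model is also not more accurate overall. Root mean squared error over the four doses, planned sequence against categorical, is 0.22–0.24 v 0.23–0.24 for the first shape and 0.15–0.16 v 0.24 if change is linear. Only the plateau with an unchanging control arm clearly favours it (0.26–0.30 v 0.24) at correlation 0.6; the first shape does so at correlation 0.8 (0.20–0.21 v 0.17–0.18). No improvement in the dose actually chosen has been shown.

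A reader might infer that the plan contradicts itself or cannot address Aim 2. The documents do not support that: nothing conflicts, and extra contrasts are not excluded. Nor should all the poor coverage be blamed on missing parameters, since two of the three non-linear shapes fit exactly within a planned curve.

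**Conclusion.** The point holds as a cheap improvement. The parameter count follows from the plan's text and does not depend on the assumed SD, correlation or final-visit code. The plain-average tie does depend on session-number time.

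A misplaced, over-narrow interval at a dose is possible by either mechanism. Its size is not fixed by the documents, because the fit criterion, random effects and time code are unstated. It is smaller when the control arm also improves or when slopes truly vary.

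It would be wrong to infer that the Go/No-Go comparison is safe from this, or that it is invalid. If the pre-to-post effect is read from a selected linear, quadratic or two-slope curve, it can shift: for a true 0.6, Step 3 gives 0.68–0.72 under the first shape and 0.50–0.57 under the plateau. Only the three-slope curve leaves the final difference free. The milestone text does not say which estimate will be used.

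**What to change.** For each outcome, add one group-by-assessment model with assessment categorical (five levels, common baseline mean) and the planned family adjustment. Use an unstructured within-person covariance, or cluster-robust standard errors if that does not converge. The covariance needs stating: with true slope variation as above, a categorical model with only a person intercept covered about 88–91% at the final visit.

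Report the CBM-I minus control difference with its 95% CI at each of the four post-baseline assessments beside the selected growth curve. Label as model-dependent any dose conclusion that holds only under the curve. Keep the growth models as planned. How the dose is read from these results is for the sponsor to set before analysis.

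The cost is SAP wording and one extra model per outcome on data already planned. The downside is imprecision. At correlation 0.6 the 8-to-16 contrast has standard error √[4(1 − 0.6)/23] = 0.26 SD, a 95% CI of about ±0.5 SD (standard error 0.19 to 0.32 for correlation 0.8 to 0.4). If change is truly linear, final-visit power is also lower than under the linear curve: 72% against 81% for 0.6 SD, and 56% against 66% for the milestone's 0.50. Adjacent doses will not be well separated, and the report should say so.

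### Milestone 1 is one pre-to-post group difference per outcome, but the SAP tests group on the slopes of a selected curve and does not say how those slopes settle the milestone

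*Combined protocol and SAP*

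**What the plan says.** The milestone section (R61 Go/No-Go Milestones for R33 Phase, criterion 1) asks for target engagement on two of the three bias outcomes, "as reflected by a significant medium effect ($d=0.50$) between groups from pre-to-post-intervention". Aim 1 predicts that "personalized CBM-I will result in significantly greater reduction of interpretation bias on at least two of three measures", and the Project Summary puts the gate the same way: "Our Go/No-Go Milestones reflects a significant difference in interpretation bias reduction between groups". Each describes one directional group comparison per outcome.

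The Statistical Analysis Plan handles target engagement and dose in one section ("Aims 1 and 2. Multilevel modeling"). It opens generally: "multilevel models will test the effects of CBM-I vs ICC group on changes in the outcome". It then expects curvature: "Given that bias change over time may not occur in a linear fashion, we will compare several alternative models for change over time". The candidates are linear, quadratic, two-slope (bend at session 9) and three-slope (bends at sessions 5 and 13). The only concrete group test on the bias outcomes follows: "Once the best-fitting model is identified for each outcome, the treatment group will be used to predict between-individual differences in slopes". The SAP's one other between-group test is the Aim 3 t-test on acceptability.

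The SAP does not state which slope or combination of slopes settles the milestone, how d is computed, whether 0.50 is a floor on the estimate, or where time zero lies for the quadratic.

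**The concern.** Slopes suit Aim 2, which assesses bias at four doses "in order to identify the optimal dose at which bias reduction occurs". The milestone asks a different question: how far apart the groups have moved by the end. With two or three slopes, a group can differ on one slope without differing in total change. It can also differ in total change without any one slope reaching significance. The move to the R33 phase depends on this verdict, so a choice among slopes made after seeing the data could alter it.

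**Working it through.** **1. What each curve's coefficients mean.** Code the five assessments as 0, 4, 8, 12 and 16 sessions completed (an assumption; the last is one week after session 16). The group difference in change from first to last assessment is then:
- Linear: 16δ. Testing δ is testing this quantity.
- Two-slope: 8δ₁ + 8δ₂.
- Three-slope: 4δ₁ + 8δ₂ + 4δ₃.
- Quadratic, time zero at session 1: 16β₁ + 256β₂.
- Quadratic, time zero at mid-course: 16β₁ + (64 − 64)β₂ = 16β₁, so here the linear term alone is the milestone quantity.

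**2. Inputs.** From the documents: N=46, the assessment times, the four curves and the two-of-three rule. They give no sample-size derivation, so there is no power figure of theirs to reproduce. Assumed: 23 per arm, unit SD, equal correlation 0.6 between assessments, two-sided 5% counted only when it favours CBM-I, and a true benefit of 0.6 SD at post. Dropout and family clustering are ignored.

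**3. Hand check: two-slope curve, separate session-1 intercepts, time scaled 0 to 1.**
- Residual variance of a difference in arm means: (2/23)(1 − 0.6) = 0.0348.
- Contrast: the sum of squares of time about its mean is 0.625. Variance 0.0348/0.625 = 0.0557, SE 0.236.
- Bend: the sum of squares of |t − 0.5| about its mean is 0.175. Variance 0.0348/0.175 = 0.199.
- Group difference in change over one half of the course: variance (0.0557 + 0.199)/4 = 0.0636, SE 0.252.
- Steady benefit, contrast: 0.6/0.236 = 2.54, pass rate Φ(2.54 − 1.96) = 72%.
- Steady benefit, each slope: 0.3/0.252 = 1.19, Φ(1.19 − 1.96) = 22%. Either slope is at most 44%; simulation gives 43%.
- 0.6 SD at session 9 and zero at post: early slope 0.6/0.252 = 2.38, Φ(0.42) = 66%. The contrast is truly zero and passes 2.5%.

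**4. Simulation: two-slope curve, 200,000 draws per cell.** Pass rates are any slope significant vs contrast.

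| Benefit | Separate intercepts | Common intercept | Common intercept, estimated d ≥ 0.50 also required |
|---|---|---|---|
| Steady to post | 43% vs 72% | 48% vs 80% | 42% vs 68% |
| Complete by session 9 | 68% vs 72% | 79% vs 80% | 58% vs 68% |
| Complete by session 5 | 65% vs 53% | 81% vs 67% | 47% vs 53% |
| Mid-course only, gone by post | 66% vs 2.5% | 77% vs 2.5% | about 1% each |

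Under the linear curve the two rules never disagree.

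**5. Sensitivity.**
- *Covariance.* Adding random slopes (SD 0.5 over the course; common intercept, no d floor) gives 44% vs 63% (steady), 74% vs 63% (complete by session 9) and 77% vs 51% (complete by session 5). The session-9 case moves from near-equal to slopes passing more often.
- *Slope rule.* For an even benefit of d=0.5 at post, over four assumed covariances, the contrast passes 0.35–0.69. Any-slope passes 0.28–0.41, Bonferroni 0.18–0.27 and all-slopes 0.001–0.018.

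**6. Bias of the contrast when the curve misfits.** Take a benefit complete by session 5, with separate intercepts. The two-slope contrast has expectation 0.6 × (−0.25 + 0 + 0.25 + 0.5)/0.625 = 0.48 against a true 0.6. With a common intercept and correlations 0.4 to 0.8 it is 0.50–0.54 under two slopes and 0.49–0.52 under the quadratic. Under three slopes it is unbiased.

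**The case against.** The strongest reply is that the milestone section already fixes the criterion, and the SAP's opening sentence on group effects on change is wide enough to include the pre-to-post contrast. On that reading the slope sentence serves the dose question, and the same fitted model supplies the contrast. This largely stands. A reader might infer that the SAP makes slope significance the Go criterion; the documents neither say so nor exclude it. If the team computes the contrast, no harm follows and the gap is one of wording.

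A reader might also infer that slope testing systematically misses real benefit, or that it invites a false Go from a passing effect. Neither holds in general. The direction depends on the slope rule, the shape of the benefit, the covariance and whether d ≥ 0.50 is also required. That requirement removes nearly all passes for an effect gone by post and reverses the session-5 comparison. It does not rescue the steady benefit (42% vs 68%).

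Curve selection also matters. If the shared curve and the benefit are both linear, selection by BIC (assumed; the SAP names no criterion) picks the linear curve 97% of the time and costs about 1 point. Large losses need a bent shared curve with a benefit of another shape, a pairing the documents give no reason to expect. Quadratic results depend on a time origin the SAP leaves open.

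Finally, the contrast has its own weakness: it is biased low when the chosen curve misfits. What survives is that, under three of the four candidate curves (the quadratic when coded from session 1), the plan followed literally does not yield the single test its Go decision needs.

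**Conclusion.** The mismatch is real and rests on the text alone: one pre-to-post quantity in the milestone, several slope coefficients in the test, and no stated link. There is no consequence if the linear curve is chosen or if the team tests the model-implied contrast. There is a consequence only if slope significance decides and a non-linear curve is selected. Under the assumptions above the verdict can then move by about 30 points in pass rate for a steady benefit, and the other way for one complete by session 5. Confidence is high in the mismatch and moderate in size and direction, since alpha, allocation, SD and correlations are all assumed. This is a cheap improvement, not a demonstrated wrong test.

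**What to change.** State that milestone 1 is judged for each outcome by one test: the model-implied CBM-I minus control difference in change from session 1 to one week after session 16. This is the length-weighted sum of the group-on-slope coefficients, or the linear plus quadratic group terms taken between the first and last assessments. So defined, it does not depend on the time origin. Report it as d with a confidence interval using a prespecified SD (the pooled session-1 SD is one option), and state whether 0.50 is a floor on the estimate. Keep individual slope tests for Aim 2 and description. Because the contrast is biased low when the curve misfits, report the same contrast from a model with time as categories as a sensitivity check.

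The cost is SAP wording and one contrast statement per model, with no new data or participants. If the linear curve is selected, the primary result is unchanged. The price is that the contrast can pass less often than slope significance alone when benefit is complete by session 5: 81 − 67 = 14 points in the common-intercept case, or 77 − 51 = 26 with random slopes. The change does not cure limited power at N=46.
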